8. TREATMENT OF PATIENTS

8.1. Study Drug Administration

Study Drug (ISIS 721744 or placebo) will be administered as a single SC injection once every 4 (Cohort A) or 8 (Cohort B) weeks by blinded study staff during on-site visits at the Study Centers or by Home Healthcare professional. Self-administration of ISIS 721744 or placebo may be allowed after dosing instructions and training are provided by qualified site personnel and home healthcare nurse is available to complete all pre-dosing procedures.

Vials of Study Drug (ISIS 721744 or placebo) are for single use only.

Please refer to the Study Drug Manual provided by the Sponsor or designee for more detailed instructions for Study Drug (ISIS 721744 or placebo) preparation and administration.

8.2. Other Protocol-Required Drugs

Patients must have access to, and the ability to use, ≥ 1 acute HAE medication(s) (e.g., plasmaderived or recombinant C1-INH concentrate or a BK2-receptor antagonist) to treat angioedema attacks. During the course of the study, the use of acute HAE medications (plasma-derived or recombinant C1-INH concentrate, BK2-receptor antagonist, or kallikrein inhibitor) to treat angioedema attacks is allowed as medically indicated. Patients can be treated with on-demand therapy as determined by their treating physician.

CONFIDENTIAL Amendment 2
12 July 2022

8.3. Other Protocol-Required Treatment Procedures

There are no other protocol-required treatment procedures.

8.4. Treatment Precautions

Protocol

There are no specific treatment precautions required.

8.5. Safety Monitoring Rules

Stopping rules are described below in Section 8.6.

Please refer also to the 'Guidance for Investigator' section of the Investigator's Brochure.

- For the purposes of safety monitoring baseline is defined as the average of the pre-dose Study Day 1 value and the last value prior to Study Day 1
- In addition to the standard monitoring of clinical safety parameters, the following guidelines are provided for the monitoring of selected parameters chosen based on preclinical and clinical observations
- In case of discrepancy between the test results from 2 sources, such as between the central and local lab, safety-mandated action must be initiated based on the more critical (lower or higher, as relevant) of the 2 values

Confirmation Guidance: At any time during the study (Treatment or Post-Treatment Periods), the initial clinical laboratory results meeting the safety monitoring criteria presented below **must be confirmed** by performing measurements (ideally in the same laboratory that performed the initial measurement) on new specimens. All new specimen collections should take place as soon as possible (ideally within 3 days of the initial collection). For stopping rules, if the initial laboratory result is observed during the Treatment Period, the results from the retest **must be available** prior to administering the next dose of Study Drug (ISIS 721744).

Re-dosing Guidance: Patients with initial laboratory test values that reach a stopping rule must not be re-dosed until the re-test results are available. In general, patients who do not meet the stopping rules based upon retest may continue dosing. However, the Investigator or designee and the Sponsor Medical Monitor (or appropriately qualified designee) should confer as to whether additional close monitoring of the patient is appropriate. If any of the stopping criteria described in Section 8.6 are met, the patient will be permanently discontinued from further treatment with Study Drug (ISIS 721744), evaluated fully as outlined below and in consultation with the Sponsor Medical Monitor or appropriately qualified designee, and will be followed up in accordance with Section 8.8 of the Protocol.

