6.2. Study/Laboratory Assessments

6.2.1. Laboratory Assessments

Laboratory analyte samples will be collected throughout the study. A list of these analytes is contained in Appendix B.

If the PLT value, serum creatinine, or liver enzyme tests are uninterpretable (e.g., due to clumping, hemolysis, or quantity not sufficient) or missing, a repeat blood specimen should be redrawn as soon as possible (ideally within 7 days) either in clinic or by Home Healthcare (if available) or local laboratory.

All PLT count results, and liver and renal function tests, must be reviewed promptly (within 48 hours of receipt) by the Investigator, or designee, to ensure that the result has not met the stopping rule.

All lab alerts received, including those related to PLT, liver, or renal function monitoring/stopping rules, are also reviewed promptly by the Sponsor and the CRO Medical Monitors who will agree on actions to be taken. Within 24 hours of receiving an actionable lab alert the CRO Medical Monitor will communicate instructions to the Investigator or designee and the study personnel by emailing them the Safety Surveillance Form that needs to be completed and signed by the Investigator or designee /study personnel and promptly returned to the Sponsor and CRO Medical Monitor. In urgent cases, such as PLTs results below 50,000/mm³, or liver or renal test results reaching a critical stopping rule, the Investigator or designee must also be contacted by phone.

Investigators or designees may, at their discretion, test specific laboratory parameters which may be prone to clotting, clumping or hemolysis (e.g., hematology samples) at their local laboratory, in addition to the required central laboratory samples. In these instances, the local laboratory results should be recorded by the site into the electronic database. Assays which are blinded should not be locally tested and recorded into the database (e.g., PKK). All lab sample results from the site's local laboratories are received by the Study Center staff per the local laboratories' standard reporting time, and should be entered as soon as possible (ideally within 1 week) into the electronic Case Report Form (eCRF) to inform the Sponsor and CRO study monitoring teams

Further information on safety monitoring and actions to be taken by the Study Investigator or designee in the event of reduced PLT count are provided in Section 8.5.3 and Section 8.6.3.

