8.5.2. Safety Monitoring Rules for Renal Function Test Results

While on treatment, all patients will have renal function tests monitored every 4 weeks during the Treatment and Follow-up Periods as per visit schedule in Appendix A.

In the event of appearance of symptoms or signs consistent with renal dysfunction such as hematuria, polyuria, anuria, flank pain, new-onset hypertension, nausea and/or anorexia, renal function should be tested as soon as possible (ideally within 3 days). Testing at a lab that is local to the patient is permissible for this purpose.

If a patient's results meet criteria 1 or 2 below, the Investigator or designee should confirm the results and initiate weekly monitoring if confirmed. If the event a persistent elevation is observed over 2 consecutive weeks, then refer to Stopping Rules for Renal Function Test Results in Section 8.6.2.

- 1. Serum creatinine increase that fulfills all of the following: \geq 0.3 mg/dL (26.5 μ mol/L) and \geq 40% above baseline creatinine values and > ULN (refer to definition of Baseline in Section Stopping Rules Section 8.6)
- 2. Proteinuria, urine protein/creatinine ratio (UPCR) > 750 mg/g for baseline values ≥ 200 mg/g, or 4 × baseline value for baseline values < 200 mg/g that are confirmed by repeated urine protein/creatinine ratio or by a quantitative total urine protein measurement of > 1.0 g/24 hours

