8.6.2. Temporary Stopping Rules for Renal Function Test Results

In the event of a persistent elevation that is observed over 2 consecutive weeks, for either of the 2 criteria below, dosing of a patient with Study Drug (ISIS 721744 or placebo) may be stopped temporarily:

- Serum creatinine increase that fulfills all of the following criteria: ≥ 0.3 mg/dL (26.5 μmol/L) and ≥ 40% above baseline creatinine values and > ULN (refer to definition of Baseline in Section 8.6)
- 2. UPCR >1000 mg/g, confirmed by a quantitative total urine protein measurement of > 1.0 g/24 hours

The possible dosing re-initiation or follow-up schedule for any events meeting either of these criteria will be determined by the Investigator or designee **in consultation with** the Sponsor Medical Monitor or designee.

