8.8. Discontinuation of Study Drug/Treatment

A patient must permanently discontinue study treatment for any of the following:

- The patient becomes pregnant. Report the pregnancy according to instructions in Section 9.5.4
- The patient withdraws consent or assent
- The patient withdraws from treatment (but does not withdraw consent or assent)
- The patient experiences an AE that necessitates permanent discontinuation of Study Drug
- The patient develops laboratory test abnormalities that meet any of the stopping rules listed in Section 8.6
- The patient experiences an AE that necessitates unblinding of the Investigator or designee or Sponsor to the patient's treatment assignment

The reason for discontinuation of Study Drug must be recorded in the eCRF and source documentation.

Patients who discontinue Study Drug will remain in the study and attend the Tx-ET Visit (Week 25 visit assessments), unless consent or assent is withdrawn. Any patient who discontinues early from the Treatment Period should be strongly encouraged to complete the Post-Treatment Period study visits, procedures and observations (see Appendix A).

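### Protocol Sections 8.5 and 8.8 make a met renal stopping rule a permanent end to treatment, while Section 8.6.2 makes it an optional, temporary pause

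*Combined protocol and SAP*

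**What the plan says.** Two general sentences set the consequence of meeting a Section 8.6 rule.

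- Section 8.5, at the end of the re-dosing guidance: "If any of the stopping criteria described in Section 8.6 are met, the patient will be permanently discontinued from further treatment with Study Drug".
- Section 8.8, lead-in: "A patient must permanently discontinue study treatment for any of the following". One of the listed reasons is: "The patient develops laboratory test abnormalities that meet any of the stopping rules listed in Section 8.6".

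The renal rule is one of the Section 8.6 rules. Its heading is "Temporary Stopping Rules for Renal Function Test Results". For a renal elevation that persists over 2 consecutive weeks, it says that dosing "dosing of a patient with Study Drug (ISIS 721744 or placebo) may be stopped temporarily". On restarting, where the Medical Monitor is also to be consulted, it says: "The possible dosing re-initiation or follow-up schedule for any events meeting either of these criteria will be determined by the Investigator or designee".

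Elsewhere the protocol treats the renal criteria as a stopping rule. Section 8.5.2 tells the investigator, once an elevation persists, "then refer to Stopping Rules for Renal Function Test Results in Section 8.6.2". Section 6.2.1 has platelet, liver and renal results reviewed promptly "to ensure that the result has not met the stopping rule".

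**The concern.** Creatinine and the urine protein/creatinine ratio are laboratory tests, so both general sentences reach them. An investigator who follows 8.5 and 8.8 ends treatment. An investigator who follows 8.6.2 may pause dosing or not, and may restart it.

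The two paths lead to different parts of the study. Under Section 8.8.1, a patient who stops early has the Treatment Early Termination assessments 28 days after the last dose and starts the 13-week Post-Treatment Period. A patient who resumes stays in the Treatment Period. That patient complies with 8.6.2 and departs from 8.5 and 8.8, so treatment disposition, and possibly the recording of a protocol deviation, depends on which section is read.

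**Working it through.** The plan gives no figure to reproduce. The check compares the texts and then counts doses.

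**Step 1. Texts side by side, for a renal elevation that meets Section 8.6.2**

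| Source | Mandatory or optional | Duration | Restart |
|---|---|---|---|
| 8.5, re-dosing guidance | Mandatory | Permanent | None |
| 8.8, laboratory bullet | Mandatory | Permanent | None |
| 8.6.2 | Optional | Temporary | Possible, after consultation |

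**Step 2. Can the texts be reconciled as written?**

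- *Renal might not be a stopping rule.* Sections 8.5.2 and 6.2.1 both treat it as one, and it sits within Section 8.6.
- *Section 8.7 might exempt it.* Section 8.7 allows dose interruptions for safety or tolerability after consultation with the Medical Monitor. It does not mention 8.6.2 and does not qualify 8.5 or 8.8.
- *The general sentences might have been written for liver.* The liver rule in 8.6.1 is a permanent stop and agrees with both. But both sentences say any rule or criterion in 8.6, without exception.

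**Step 3. Doses at stake**

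Dosing days (Appendix A): Cohort A on Days 1, 29, 57, 85, 113 and 141; Cohort B on Days 1, 57 and 113. The first scheduled on-treatment laboratory sample is on Day 29.

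Assumptions: the elevation is first seen at a scheduled visit, any dose due that day is given, and the rule is met 14 days later.

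- Day the rule is met: 29 + 14 = 43.
- Cohort A, permanent stop: 6 − 2 = 4 doses forgone (Days 57, 85, 113, 141).
- Cohort B, permanent stop: 3 − 1 = 2 doses forgone (Days 57, 113).

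For a first elevation on Day 57, 85, 113 or 141, the rule is met on Day 71, 99, 127 or 155. A permanent stop then forgoes 3, 2, 1 or 0 doses in Cohort A and 1, 1, 0 or 0 in Cohort B.

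The difference between a permanent stop and a pause is the number of doses still given after the pause. The documents give no pause length and no rule for delayed doses, so both are varied here for a rule met on Day 43:

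| Pause | Skipped doses not made up | Schedule shifted to restart when the pause ends |
|---|---|---|
| 28 days (to Day 71) | A: Days 85, 113, 141 = 3; B: Day 113 = 1 | A: Days 71, 99, 127, 155 = 4; B: Days 71, 127 = 2 |
| 56 days (to Day 99) | A: Days 113, 141 = 2; B: Day 113 = 1 | A: Days 99, 127, 155 = 3; B: Days 99, 155 = 2 |

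The shifted schedules also assume that dosing up to Day 155, before the Day 169 visit, is permitted. Over these cases the difference is 2 to 4 doses in Cohort A and 1 to 2 in Cohort B. If the optional pause is not used at all, it is 4 and 2.

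**Step 4. How often**

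Section 2.5.1 reports that no renal, liver or bleeding rule was met in Phase 2. The plain-language results summary reports 1 of 90 participants stopping treatment for a medical problem. It does not say that the problem was renal and does not count pauses, so it does not estimate the renal event rate.

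**The case against.** The best defence is that the specific rule governs the general one: a section headed as temporary shows what was intended for renal events, and the Medical Monitor is consulted before any restart, so sites are unlikely to diverge much. The intention may well be that. But the protocol has no precedence clause, and consultation under 8.6.2 offers a restart that 8.5 and 8.8 do not allow. The defence lowers the practical risk and leaves the text contradictory.

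It is also fair to say that 8.5 and 8.8 state one general rule, since 8.5 sends the patient's follow-up to 8.8. This is one renal contradiction, not two.

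Three stronger readings are tempting, and the documents do not support them.

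- *The bleeding rule is equally contradicted.* Section 8.6.4 makes a permanent stop optional and leaves resumption open, which conflicts with 8.5 read literally. But the 8.5 sentence closes a paragraph about laboratory retests, and the 8.8 bullet is limited to laboratory abnormalities. A laboratory-only reading removes the conflict.
- *The platelet rule is contradicted too.* Section 8.6.3 only points to Table 2 and does not label which rows are stopping criteria. Table 2 nevertheless gives a dosing action for every row, and 8.7 makes the table binding. That is a labelling matter.
- *The efficacy analysis is compromised.* The primary estimand in SAP Section 3.2.2 uses a treatment policy strategy, with attacks collected to Week 25 whatever happens to treatment. Exclusion from the Per-Protocol Set requires a major deviation that could compromise the interpretation of efficacy (SAP Section 4.5). That is possible for such a patient but is not shown.

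**Conclusion.** The contradiction is real and confined to the renal rule. For an elevation persisting over 2 consecutive weeks, Sections 8.5 and 8.8 require permanent discontinuation, while Section 8.6.2 permits a temporary stop with possible re-initiation.

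The largest effect for an elevation first seen at a scheduled visit is 4 of 6 doses in Cohort A or 2 of 3 in Cohort B, for a rule met on Day 43. It falls to none late in the Treatment Period. The difference from a pause rests on assumptions about pause length and make-up doses and should not be quoted as a single figure.

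Few patients are likely to be affected. Power, alpha and the primary analysis are unchanged. The point still deserves correction because it concerns a safety instruction that gives opposite outcomes for the same patient. The overlap with bleeding is a secondary wording note.

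**What to change.** Reconcile Sections 8.5 and 8.8 with Section 8.6.2: label each Section 8.6 rule once as permanent or temporary, and make the general sentences apply only to the rules intended as permanent. In the same edit, state whether the 8.5 sentence covers laboratory rules only, which settles its relation to 8.6.4. Which clinical rule applies is for the sponsor to decide.

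The cost is wording in an amendment or clarification letter, with no extra visits or patients. The plain-language summary says that the study ended in November 2023, so new wording can no longer guide dosing here. For this study, the sponsor can document which reading governed any renal case and how it was classified for disposition and deviations, and correct the text before it is reused.

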8.5.1. Safety Monitoring Rules for Liver Chemistry Tests

The following rules are adapted from the draft guidance for industry, "Drug-Induced Liver Injury: Premarketing Clinical Evaluation," issued by the U.S. Department of Health and Human Services, Food and Drug Administration, July 2009. For a definition of Baseline please refer to guidance in Section 8.5 above.

All patients will have liver chemistry tests monitored every 4 weeks during the Treatment Period. Upon completion of the study Treatment Period, liver chemistry tests should be monitored as per visit schedule in Appendix A.

In the event of appearance of symptoms or signs of hepatic injury (jaundice, fatigue, nausea, vomiting, right upper quadrant pain or tenderness, fever, rash, abnormal bleeding or bruising, or eosinophilia > ULN) liver enzymes and bilirubin should be tested as soon as possible (ideally within 3 days). Testing at a lab that is local to the patient is permissible for this purpose.

In the event of an ALT or AST measurement that is $> 3 \times \text{ULN}$ (or the greater of $2 \times \text{baseline}$ value or $3 \times \text{ULN}$ if the baseline value was > ULN) at any time during the study (Treatment or Post-Treatment Period), the initial measurement(s) should be confirmed as described above. Additional confirmatory measurements should also be performed if ALT or AST levels increase to $5 \times \text{ULN}$.

Frequency of Repeat Measurements: Patients with confirmed ALT or AST levels $> 3 \times \text{ULN}$ (or the greater of 2 × baseline value or 3 x ULN if the baseline value was > ULN) should have their liver chemistry tests (ALT, AST, Alkaline Phosphatase (ALP), international normalized ratio [INR], and total bilirubin) retested at least once-weekly until ALT and AST levels become $\le 1.2 \times \text{ULN}$ or $1.2 \times \text{baseline}$ value if the baseline value was > ULN].

Further Investigation into Liver Chemistry Elevations: For patients with confirmed ALT or AST levels $> 3 \times \text{ULN}$ (or the greater of $2 \times \text{baseline}$ value or $3 \times \text{ULN}$ if the baseline value was > ULN), the following evaluations should be performed:

- 1. Obtain a more detailed history of symptoms and prior and concurrent diseases
- 2. Obtain further history for concomitant drug use (including nonprescription medications, herbal and dietary supplement preparations), alcohol use, recreational drug use, and special diets
- 3. Obtain a history for exposure to environmental chemical agents and travel
- 4. Serology for viral hepatitis (hepatitis A virus immunoglobulin M [IgM], hepatitis B surface antigen [HBsAg], Hepatitis C Virus antibody, cytomegalovirus IgM, and EBV antibody panel)
- 5. Serology for autoimmune hepatitis (e.g., antinuclear antibody [ANA])

Additional liver evaluations, including gastroenterology/hepatology consultations, hepatic computerized tomography (CT) or magnetic resonance imaging (MRI) scans, may be performed at the discretion of the Investigator or designee, in consultation with the Sponsor Medical Monitor. Repetition of the above evaluations should be considered if a patient's ALT and/or AST levels reach 5 × ULN.

The Study Drug must be interrupted until all evaluations and consultation with the Sponsor Medical Monitor is complete.

All lab alerts for abnormal liver function tests must be promptly reviewed by the Investigator or designee (within 48 hours of receipt) and Medical Monitor(s) (within 24 hours of receipt) as described in Section 6.2.1.

Lab alerts for abnormal liver chemistry tests will be issued for: 1) ALT or AST > $3 \times ULN$; 2) ALT or AST > $2 \times baseline$; 3) total bilirubin > ULN. These alert levels are set to anticipate the risk of a combined elevation of aminotransferases and bilirubin as per the FDA Guidance referenced in Section 8.5 above.

8.5.2. Safety Monitoring Rules for Renal Function Test Results

While on treatment, all patients will have renal function tests monitored every 4 weeks during the Treatment and Follow-up Periods as per visit schedule in Appendix A.

In the event of appearance of symptoms or signs consistent with renal dysfunction such as hematuria, polyuria, anuria, flank pain, new-onset hypertension, nausea and/or anorexia, renal function should be tested as soon as possible (ideally within 3 days). Testing at a lab that is local to the patient is permissible for this purpose.

If a patient's results meet criteria 1 or 2 below, the Investigator or designee should confirm the results and initiate weekly monitoring if confirmed. If the event a persistent elevation is observed over 2 consecutive weeks, then refer to Stopping Rules for Renal Function Test Results in Section 8.6.2.

- 1. Serum creatinine increase that fulfills all of the following: \geq 0.3 mg/dL (26.5 μ mol/L) and \geq 40% above baseline creatinine values and > ULN (refer to definition of Baseline in Section Stopping Rules Section 8.6)
- 2. Proteinuria, urine protein/creatinine ratio (UPCR) > 750 mg/g for baseline values ≥ 200 mg/g, or 4 × baseline value for baseline values < 200 mg/g that are confirmed by repeated urine protein/creatinine ratio or by a quantitative total urine protein measurement of > 1.0 g/24 hours

8.5.3. Safety Monitoring Rules for Platelet Count Results

Platelet count will be monitored at least every 4 weeks during the Treatment and Post-Treatment Periods as per visit schedule in Appendix A.

The Investigator or the designee should review all PLT count results within 48 hours of receipt. Any unreportable PLT count result must be rechecked ideally within 7 days and determined not to have met a stopping rule before dosing can continue.

Actions to be taken in the event of reduced PLT count are shown in Table 2.

Protocol

Platelet count (K/mm³)	Dosing	Monitoring frequency
≥ 125	No action	At least every 4 weeks.
> 100 to < 125	Dosing every 4 (Cohort A) or 8 (Cohort B) weeks should be continued.	At least every 2 weeks until 2 successive values > 125K/mm ³ .
$\geq 75 \text{ to} \leq 100$	Dosing every 4 (Cohort A) or 8 (Cohort B) weeks may be continued if approved by the Sponsor Medical Monitor.	Every week until 2 successive values > 100K/mm³. Consider more frequent monitoring if additional risk factors for bleeding are present.*
≥ 50 to < 75	Pause dosing. When PLT count returns to > 100K/mm ³ , restart dosing only if approved by the Sponsor Medical Monitor.	Twice weekly until 2 successive values > 75K/mm³, then weekly until 2 successive values > 100K/mm³. Consider more frequent monitoring if additional risk factors for bleeding are present.*
≥ 25 to < 50	Permanently discontinue Study Drug. Consider corticosteroids if additional risk factors for bleeding are present.**	Twice weekly until 2 successive values > 75K/mm³, then weekly until 2 successive values > 100/mm9. Consider more frequent monitoring if additional risk factors for bleeding are present.*
< 25	Permanently discontinue Study Drug. Corticosteroids strongly recommended.**	Daily until 2 successive values > 25K/mm³, then twice weekly until 2 successive values > 75K/mm³, then weekly until 2 successive values > 100K/mm³. Consider more frequent monitoring if additional risk factors for bleeding are present.*

^{*} The suitability of the patient for interrupted and/or continued dosing will be determined by the Investigator or designee in consultation with the Medical Monitor and will be based on factors such as the original rate of decline in the patient's PLT count, whether any bleeding events were experienced by the patient, and the speed of recovery of PLT count after interruption of dosing.

There will be lab alerts for PLT values under 100,000/mm³.

^{**} Recovery in platelet count may be accelerated by administration of high-dose glucocorticoids. Treatment as recommended by the American Society of Hematology (ASH) (2019) guidelines for immune thrombocytopenia (Blood Advances, 10 DECEMBER 2019, Volume 3, Number 23) includes initial therapy with either dexamethasone 40 mg per day for 4 days, or prednisone 0.5 to 2.0 mg/kg per day. Prednisolone or prednisone may be administered for up to 2 to 4 weeks with taper; alternatively, intravenous immunoglobulin (IVIG) may be administered at 0.4 g/kg/d for 5 days, or infusions of 1 g/kg/d for 1-2 days (Provan et al. 2010; Provan et al. 2019).

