For platelet (K/mm³), the number and percentage of patients falling in each of the following categories based on the confirmed results (both central and local lab data will be used) will be tabulated by treatment group for ≥ 125 , ≥ 100 to < 125, ≥ 75 to ≤ 100 , ≥ 50 to < 75, ≥ 25 to < 50, < 25.

A confirmed value is based on a consecutive lab value within 7 days. If that value is in the same or worse category the initial value is confirmed. If the consecutive value is in a better category, then the initial value is confirmed using the consecutive value category. If there is no retest within 7 days, then the initial value is presumed confirmed. If there are multiple results on the same day, no matter from the same lab vendor or different lab vendors, then the worst value will be utilized in the analysis.

Laboratory data will be presented in by-patient listings.

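### SAP platelet categories overlap at exactly 100 K/mm³ and differ from protocol Table 2; at the same value, Table 2 and the lab-alert sentence need reconciling

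*Combined protocol and SAP*

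**What the plan says.** **SAP 4.10.4 (Clinical Laboratory Evaluation).** Patients are to be counted by treatment group in six platelet categories, using confirmed results from central and local laboratories. The categories are listed in the text, and two neighbouring ones read "≥ 100 to < 125, ≥ 75 to ≤ 100" K/mm³. The same paragraph defines confirmation. A retest within 7 days in the same or a worse category confirms the first value. A retest in a better category moves the patient to that better category. With no retest within 7 days, the first value stands.

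**Protocol 8.5.3, Table 2.** The corresponding rows are > 100 to < 125 (dosing should continue) and ≥ 75 to ≤ 100. In the lower row, dosing every 4 or 8 "weeks may be continued if approved by the Sponsor Medical Monitor", with weekly counts.

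**Alerts and review.** Protocol 8.5.3 states: "There will be lab alerts for PLT values under 100,000/mm³". Under protocol 6.2.1, lab alerts "are also reviewed promptly by the Sponsor and the CRO Medical Monitors who will agree on actions to be taken". Protocol 8.5.3 also says: "The Investigator or the designee should review all PLT count results within 48 hours of receipt".

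**The concern.** The SAP list appears to be the reporting counterpart of Table 2: it has the same six rows, with one bound changed from > to ≥. That change makes two categories share a value. The programmer must then choose a row for a count of 100 by a rule the SAP does not state, and the choice may not match the row that governed the patient's dosing. The confirmation rule depends on telling the same category from a better one, so the overlap also reaches patients whose first count was not 100 but whose retest was. This is the arm-level summary of a risk the protocol monitors with its own action table, so its rows should be unambiguous.

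A second, smaller mismatch sits at the same value. Table 2 asks for Sponsor Medical Monitor approval at exactly 100,000/mm³, but the alert that brings results to the Medical Monitors is stated only for lower values.

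**Working it through.** The plan gives no figure to reproduce, so the check is of the boundaries themselves.

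**Step 1: which categories hold each value.** The six intervals in each document were written as inequalities and tested on every whole number from 0 to 400 K/mm³.

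| List | Values in more than one category | Values in none | Where 100 falls |
|---|---|---|---|
| Protocol Table 2 | none | none | ≥ 75 to ≤ 100 only |
| SAP 4.10.4 as printed | 100 | none | ≥ 75 to ≤ 100 and ≥ 100 to < 125 |
| SAP with > 100 to < 125 | none | none | ≥ 75 to ≤ 100 only |

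**Step 2: the SAP confirmation rule at 100.**

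- First value 90, retest 100. If 100 belongs to the lower row, the retest is in the same category and the patient stays in ≥ 75 to ≤ 100. If it belongs to the upper row, the retest is in a better category and the patient moves to ≥ 100 to < 125. The same holds for any first value from 75 to 99.
- First value below 75, retest 100. The retest is better on either reading, but the category it confirms is not unique.
- First value 100, no retest within 7 days. The value is presumed confirmed, in two rows.

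**Step 3: alert against approval row.**

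| Count (K/mm³) | Alert (below 100,000/mm³) | Table 2 row needing approval (≥ 75 to ≤ 100) |
|---|---|---|
| 99 | yes | yes |
| 99.999 | yes | yes |
| 100 | no | yes |
| 100.001 | no | no |
| 101 | no | no |

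The two rules differ at exactly 100,000/mm³ and nowhere else around that boundary.

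**Step 4: size in the table.** Planned arm sizes in protocol 10.2 are 42 (every 4 weeks), 21 (every 8 weeks) and 21 (pooled placebo). One patient assigned to one row rather than the other changes that row by 1/42 = 2.4 percentage points, or 1/21 = 4.8. This is the size per affected patient; the documents do not say how many to expect.

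**The case against.** Little may turn on this. Entry excludes counts below 130 K/mm³ (protocol 5.2), protocol 2.5.1 reports no platelet signal in the ongoing Phase 2 extension, and the result must be exactly 100. That is fair and is why the point is minor.

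The SAP bound could be deliberate: protocol Appendix D grades 100,000 as moderate and only lower counts as severe. But the SAP's lower row still includes 100, so the overlap remains, and SAP 4.16 lists no intended departure from Table 2. It could also be a symbol lost in reproduction; Table 2 itself shows a damaged unit in the published text. That cannot be excluded without the signed SAP.

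Three stronger readings are tempting and are not supported.

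- *A patient at 100 will be counted twice.* The confirmation rule presupposes one ordered category per patient, and a program that assigns rows in sequence would yield one row. What the SAP leaves open is which row.
- *A patient at 100,000 could be dosed without anyone noticing.* The Investigator must review every platelet result within 48 hours, alert or not, and Table 2 then directs the Investigator to the Sponsor Medical Monitor. Nothing makes the alert the only route to approval.
- *Alerts should also cover counts below 125.* In the > 100 to < 125 row dosing continues without a Medical Monitor decision, and the documents do not promise an alert for every row with extra monitoring.

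**Conclusion.** The point holds as a minor correction. As printed, the SAP platelet categories are not mutually exclusive at 100 K/mm³ and do not match Table 2, and the confirmation rule gives two answers for a retest of 100. One boundary value is affected. Any effect on a reported percentage is one patient's worth per occurrence, with frequency unknown but likely low given the entry limit. This assumes that the ≥ sign is in the signed SAP and that the list is meant to summarise Table 2, as its other five rows indicate.

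The alert mismatch is literal but narrower still: at exactly 100,000/mm³ the automatic prompt to the Medical Monitors is absent, while the Investigator's review and the Table 2 instruction remain. It is a matter of alignment between two sentences, not evidence of an unmonitored risk.

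**What to change.** In SAP 4.10.4, make the platelet categories mutually exclusive and identical to the protocol Table 2 rows they summarise. As Table 2 stands, the second category becomes > 100 to < 125. Check the symbol against the signed SAP first. The cost is one character and the matching line of table programming; it also settles the confirmation rule, with no further text.

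Separately, the sponsor should reconcile Table 2 with the lab-alert sentence in protocol 8.5.3 for a count of exactly 100,000/mm³. Which passage changes, and to what value, is for the clinical team. If Table 2 moves, the SAP categories should follow it.
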